#### 4.4.2 Data Collection and Follow-up for Withdrawn Subjects

Even though a subject has withdrawn from the study, follow-up and survival data on such subjects throughout the protocol defined follow-up period will still need to be collected if possible. Such data is important to the integrity of the final study analysis since early withdrawal could be related to the safety profile of the study device. If a subject withdraws consent to participate in the study, for subject safety reasons, attempts will be made to obtain permission to collect follow up information whenever possible.

#### 4.5 Description

Biomonitor 3 is a programmable, subcutaneous insertable monitor able to record subcutaneous ECGs (sECGs) and other physiological parameters.

The Biomonitor 3 is designed to automatically record the occurrence of arrhythmias in a patient. Arrhythmia may be classified as atrial fibrillation (AF), bradyarrhythmia, asystole, sudden rate drop, or high ventricular rate. In addition, the Biomonitor 3 can be activated by the patient to record cardiac rhythm during symptomatic episodes.

The Biomonitor 3 system consists of three main components:

 Biomonitor 3 insertable cardiac monitor - The Biomonitor 3 is a small, leadless device that is typically inserted under the skin, in the chest. The device uses two electrodes on the body of the device to continuously monitor the patient's subcutaneous ECG. The device memory can store up to 30 min of subcutaneous ECG (sECG) recordings from automatically detected arrhythmias and up to 30 min of sECG recordings from patient-triggered episodes. When a patient experiences symptoms, the sECG recordings can be manually triggered by placing the Remote Assistant III over the Biomonitor 3. The insertable monitor is provided preloaded in an insertion tool. An incision tool is also provided.

Note - The Biomonitor 3 subcutaneous ECG may differ from a surface ECG due to differences in electrode separation and device placement in the body. Biomonitor 3 detects a subcutaneous ECG from a pair of electrodes. These signals are filtered in two different ways. For detection of QRS complexes, the signals are filtered with a passband of 10-40 Hz in order to suppress T-waves, artifacts, and baseline drift at low frequencies, and myoptentials and EMI at high frequencies. The resulting signal is appropriate for QRS detection as other components of the signal have been suppressed. This signal naturally does not have a typical ECG morphology due to the bandpass. For waveform display (real-time streaming sECG with the physician's programmer and snapshots for review by the physician), a different passband is 0.5 – 40 Hz, which is designed to retain morphological features of a typical ECG while still rejecting large low frequency artifacts and baseline drift.

- 2. BIOTRONIK Renamic / ICS 3000 Programmer The programmer is used to set up the Biomonitor 3 to detect arrhythmias. It also allows you to view, save, or print the stored information.
- 3. BIOTRONIK CardioMessenger® Smart is a telemetry patient device that forwards the data from the Biomonitor 3 to BIOTRONIK's Home Monitoring Service Center.

Biomonitor 3 may be used with BIOTRONIK Home Monitoring® technology, which is an automatic, wireless, remote monitoring system for management of patients with insertable cardiac monitors. When active, Home Monitoring enables the exchange of information about a patient's cardiac status from the implant. The information is transmitted to the Home Monitoring Service Center (HMSC), where the physician may log in to review. The HMSC can be used to provide the physician with advanced reports from the implanted device and process them into a graphical and tabular format. This information may help the physician optimize the therapy process, possibly providing earlier notification of clinically relevant events to help guide future therapy.

• BIOTRONIK conducted the TRUST study to evaluate the safety and effectiveness of Home Monitoring. With the TRUST study, BIOTRONIK was able to show the following with regards to Home Monitoring:

- BIOTRONIK Home Monitoring information may be used as a replacement for device interrogation during in-office follow-up visits.
- A strategy of care using BIOTRONIK Home Monitoring with office visits when needed has been shown to extend the time between routine, scheduled in-office follow-ups of BIOTRONIK implantable devices in many patients. Home Monitoring data is helpful in determining the need for additional in-office follow-up.
- BIOTRONIK Home Monitoring provides early detection of arrhythmias.
- BIOTRONIK Home Monitoring provides early detection of silent, asymptomatic arrhythmias.
- Automatic early detection of arrhythmias and device system anomalies by BIOTRONIK Home Monitoring allows for earlier intervention than conventional in-office follow-ups.
- BIOTRONIK Home Monitoring allows for improved access to patient device data compared to conventional in-office follow-ups since device data is automatically collected and reported on a daily basis.
- The implanted device's Home Monitoring function can be used for the entire operational life of the implanted device (prior to ERI).
- NOTE: When ERI mode is reached, this status is transmitted and Home Monitoring® will be discontinued after two weeks.

**Electromagnetic Interference (EMI)** - Precautions for EMI interference with the Biomonitor 3 insertable cardiac monitors including cellular telephones, electronic article surveillance systems, and others.

**Use in Cellular Phone Restricted Areas** - The mobile patient device (transmitter/receiver) should not be utilized in areas where cellular phones are restricted or prohibited (i.e., commercial aircraft).

**Elective Replacement Indicator (ERI)** - When ERI mode is reached, this status is transmitted. Home Monitoring data transmissions will continue for another 2 weeks. After 2 weeks, data will no longer be transmitted to the Service Center.

**Communication Loss** - A system alert appears in the physician's queue on the Home Monitoring website if no data transmissions occur for a period of time programmed by the user. You may configure alerts so that an SMS, fax and/or e-mail message is sent to the physician regarding the communication loss. If no data transmissions have been received by HMSC after 90 days, the patient will be deactivated. In the event of sustained communication loss, an in-office follow-up visit is recommended.

#### 4.6 Preparation and Administration/Implantation and Explantation of Device

#### **Preparation of Device**

The Biomonitor 3 is preloaded in the insertion tool and is packaged with an incision tool in a single container sterilized with ethylene oxide. The device can be implanted in an office setting and all implantations for the study will be performed in the Clinical Research Trials Unit (CRTU). The implantation procedure is performed with injection of a local anesthetic (lidocaine). Conscious sedation is not required.

Peel off the sealing paper of the outer container as indicated by the arrow.

#### Insertion

The FIT OneStep Tool allows an "injection-like" insertion of the implant using a single tool. It is used for forming the device tunnel and subsequent subcutaneous delivery of the Biomonitor 3 implant. The Biomonitor 3 implant is provided preloaded into the blue tunneling end of FIT OneStep tool,

which has a rigid clam-shell design. There is a small window over the BIOMONITOR III implant to allow the physician to see the implant in the FIT OneStep tool. The incision tool and FIT OneStep tool are intended for single use.

Incision and FIT OneStep tools

Biomonitor 3has been developed to be inserted in a close-fitting subcutaneous tunnel, preferably in or around the left side of the chest. Recommended locations are those areas close to the heart where the implant will be exposed to minimal movement from body positional changes or from arm movement. Suitable implant locations are shown below. In position A, a location between the suprasternal notch and the left nipple is shown. Position B shows an implant location of approximately 45° with respect to the midline. The choice of placement location is to be decided by the physician, on the basis of individual patient anatomy and comfort, as well as cosmetic considerations. The insertion process consists of four (4) intuitive steps: Incision, Tunneling, Unlocking and Retraction

Two recommended positions for the placement for Biomonitor 3

Biomonitor 3 insertion procedure

#### Explantation

Explantation will be performed in the CRTU or the HRS Lab. Local anesthetic is injected into the previous incision site. Gentle traction is applied to the device and the device is removed.

#### 4.7 Subject Compliance Monitoring

All patients will undergo Home Monitoring of their device. By default, the Biomonitor 3 will transmit all data and a daily trend report between 1:00 A.M. and 2:00 A.M. daily. BIOTRONIK's Home Monitoring system is also designed to notify clinicians in less than 24 hours of changes to the patient's condition or status of the inserted device. Updated data may not be available if:

- The patient's CardioMessenger is off or damaged and is not able to connect to the Home Monitoring Service Center.
- The CardioMessenger cannot establish a connection to the inserted device.
- The telephone and/or Internet connection do not operate properly
- The Home Monitoring Service Center is off-line (upgrades are typically completed in less than 24 hours)

These updates will help to assist the subject to make the necessary changes so that data can be transmitted and they are not lost to follow up.

#### 4.8 **Prior and Concomitant Therapy**

Patients may continue on standard of care medical therapy for amyloidosis and any other medical therapy needed.

Patients enrolled in the study with an implanted Biomonitor 3 need careful assessment prior to undergoing one of the following procedures. A detailed analysis of the advantages and risks should be made. Cardiac activity during one of these procedures should be confirmed by continuous monitoring of peripheral pulse or blood pressure. Following the procedures, insertable cardiac monitor function must be checked.

**Therapeutic Diathermy Equipment** - Use of therapeutic diathermy equipment is to be avoided for insertable cardiac monitor patients due to possible heating effects of the insertable cardiac monitor and at the implant site. If diathermy therapy must be used, it should not be applied in the immediate vicinity of the insertable cardiac monitor. The patient's peripheral pulse should be monitored continuously during the treatment.

**Transcutaneous Electrical Nerve Stimulation (TENS)** - Transcutaneous electrical nerve stimulation may interfere with insertable cardiac monitor function. If necessary, the following measures may reduce the possibility of interference:

Place the TENS electrodes as close to each other as possible. Place the TENS electrodes as far from the insertable cardiac monitor as possible. Monitor cardiac activity during TENS use. **Defibrillation** - The following precautions are recommended to minimize the inherent risk of insertable cardiac monitor operation being adversely affected by defibrillation:

The paddles should be placed anterior-posterior or along a line perpendicular to the axis formed by the insertable cardiac monitor

The energy setting should not be higher than required to achieve defibrillation.

**Radiation** - Insertable cardiac monitor electronics may be damaged by exposure to radiation during radiotherapy. To minimize this risk when using such therapy, the insertable cardiac monitor should be protected with local radiation shielding.

**Lithotripsy** - Lithotripsy treatment should be avoided for insertable cardiac monitor patients since electrical and/or mechanical interference with the insertable cardiac monitor is possible. If this procedure must be used, the greatest possible distance from the point of electrical and mechanical strain should be chosen in order to minimize a potential interference with the insertable cardiac monitor.

**Electrocautery** - Electrocautery should never be performed within 15 cm (6 inches) of an insertable cardiac monitor because of the danger of damaging the insertable cardiac monitor. When possible, a bipolar electrocautery system should be used.

**Transurethral resection of the prostate** - It is recommended that the cautery ground plate be placed under the buttocks or around the thigh, but not in the thoracic area where the current pathway could pass through or near the cardiac monitor.

Importantly, the device is **MR Conditional -** The cardiac monitor is labeled and certified MR conditional.

The following requirements must always be fulfilled in order to perform an MR scan using BIOTRONIK's BioMonitor 3:

- 1. There are no other active or abandoned cardiac implants (e.g., lead extensions, lead adapters or abandoned leads) in the patient's body.
- 2. Other active or passive implants are permitted if they are identified as MR conditional by the manufacturer. NOTE: An MRI scan is permitted only if the product-specific conditions are met for all implants and if no metal insertable device longer than 5 cm is in the vicinity of the BIOTRONIK cardiac monitor within a distance of less than 4 cm.
- 3. The device is located in the patient's chest area.

The MRI scanner has to meet the following conditions:

- 1. Use of a clinical MRI system with a cylindrical bore and a static magnetic field strength of:
  - a. 1.5 Tesla (for BioMonitor and BioMonitor 3) or 3.0 Tesla quadrature transmit coils
  - b. only (for BioMonitor 2).
- 2. The slew rate of the MRI scanner's gradient fields should not exceed 200 T/m/s per axis.
- 3. For the head and the extremities, local transmitter and receiver coils are approved for use in addition to the local receiver coils.
- 4. Only local receiver coils may be used for the thorax.

- 5. Maximum spatial gradient of the static magnetic field specification must be  $\leq 100$  T/m (10,000 gauss/cm).
- 6. Under worst case conditions, the BioMonitor 3 is expected to produce a maximum temperature rise of <4.5° C after 30 minutes of continuous scanning.
- 7. Image artifact and distortion can result from the presence of the BioMonitor 3 device within the field of view. Image artifact and distortion resulting from the presence of the device within the field of view must be considered when selecting the field of view and imaging parameters. These factors must also be considered when interpreting the MRI images.

The following conditions must be met during the MR scan:

- 1. The MR scan should be performed with the patient in supine position.
- 2. The mean specific absorption rate (SAR) for the whole body as displayed by the MRI scanner must not exceed 4.0W/kg.
- 3. The head absorption rate displayed by the MR scanner must not exceed 3.2 W/kg.

#### **Environmental factors**

The operation of any insertable cardiac monitor can be affected by certain environmental sources generating signals that resemble cardiac activity. In some cases the disturbance sources can couple sufficient energy to damage the insertable cardiac monitor.

BIOTRONIK insertable cardiac monitors have been designed to significantly reduce susceptibility to disturbance sources. However, due to the variety and complexity of sources creating interference, there is no absolute protection against disturbance sources. Generally, it is assumed that disturbance sources produce only minor effects, if any, in insertable cardiac monitor patients. If the patient presumably will be exposed to one of the following environmental conditions, then the patient should be given the appropriate warnings.

The following equipment (and similar devices) may affect normal insertable cardiac monitor operation: electric arc welders, electric melting furnaces, radio/television and radar transmitters, power generating facilities, high voltage transmission lines, electrical ignition systems (also of gasoline powered devices) if protective hoods, shrouds, etc., are removed, electrical tools, anti-theft devices of shopping centers and electrical appliances, if not in proper condition or not correctly grounded and encased.

Patients should exercise reasonable caution in avoidance of devices which generate a strong electric or magnetic field. Some potential EMI sources include:

**High Voltage Power Transmission Lines** - High voltage power transmission lines may generate enough EMI to interfere with insertable cardiac monitor operation if approached too closely.

**Home Appliances** - Home appliances normally do not affect insertable cardiac monitor operation if the appliances are in proper condition and correctly grounded and encased. There are reports of insertable cardiac monitor disturbances caused by electrical tools and by electric razors that have touched the skin directly over the insertable cardiac monitor.

**Communication Equipment** - Communication equipment such as microwave transmitters, linear power amplifiers, or high-power amateur transmitters may generate enough EMI to interfere with insertable cardiac monitor operation if approached too closely.

**Commercial Electrical Equipment** - Commercial electrical equipment such as arc welders, induction furnaces, or resistance welders may generate enough EMI to interfere with insertable cardiac monitor operation if approached too closely.

**Electrical Appliances** - Electric hand-tools and electric razors (used directly over the skin of the insertable cardiac monitor) have been reported to cause insertable cardiac monitor disturbances. Home appliances that are in good working order and properly grounded do not usually produce enough EMI to interfere with the insertable cardiac monitor operation.

**Electronic Article Surveillance (EAS)** - Equipment such as retail theft prevention systems may interact with the insertable cardiac monitor devices. Patients should be advised to walk directly through and not to remain near an EAS system longer than necessary. **Cell Phones** - Recent studies have indicated there may be a potential interaction between cellular phones and insertable cardiac monitor operation. Potential effects may be due to the radio frequency signal when the phone is within close proximity (within 6 inches [15 centimeters]) to the insertable cardiac monitor. Based on testing to date, effects resulting from an interaction between cellular phones and the insertable cardiac monitors have been temporary. Simply moving the phone away from the inserted device will return it to its previous state of operation.

To minimize such interactions, patients having an inserted cardiac monitor who operate a cellular phone should:

- Maintain a minimum separation of 6 inches (15 centimeters) between a hand-held personal cellular phone and the inserted device. Portable and mobile cellular phones generally transmit at higher power levels compared to hand held models. For phones transmitting above 3 watts, maintain a minimum separation of 12 inches (30 centimeters) between the antenna and the inserted device.
- Patients should hold the phone to the ear opposite the side of the inserted device. Patients should not carry the phone in a breast pocket or on a belt over or within 6 inches (15 centimeters) of the inserted device as some phones emit signals when they are turned ON but not in use (i.e., in the listen or standby mode). Store the phone in a location opposite the side of the cardiac monitor.

#### 4.9 Packaging and Labeling

The insertable monitor is shipped in a cardboard box, equipped with a quality control seal, and product information label. The label contains the model specifications, technical data, serial number, expiration date, and sterilization and storage information of the insertable monitor. The box contains a double container with the insertable monitor and product documentation.

The insertable monitor and its accessories have been sealed in a container and gas sterilized with ethylene oxide. To assure sterility, the container should be checked for integrity prior to opening. If a breach of sterility is suspected, return the insertable monitor to BIOTRONIK.

The insertable monitor is packaged in two plastic containers, one within the other. Each is individually sealed and then sterilized with ethylene oxide. Due to the double packing, the outside of the inner container is sterile and can be removed using standard aseptic technique and placed on the sterile field.

#### 4.10 Receiving, Storage, Distribution and Return

#### 4.10.1 Receipt of Devices

The Biomonitor 3 devices will be delivered directly to the study staff where they will be stored and inventoried. Biotronik will ship the devices directly to the study staff. The devices will be stored in the study staff offices. Study staff will record receipt in the device accountability log.

The designated study staff will count and verify that the shipment contains all the items noted in the shipping invoice. Any discrepancies, damaged or unusable devices in a given shipment will be documented in the study files. The sponsor-investigator will notify the supplier immediately of any discrepancies, damaged or unusable products.

#### 4.10.2 Storage

**Storage (temperature)** - Recommended storage temperature range is -10° to 45°C (14°-113°F). Exposure to temperatures outside this range may result in insertable cardiac monitor malfunction.

**Temperature Stabilization** - Allow the device to reach room temperature before programming or implanting the device. Temperature extremes may affect the initial device function.

**Storage** - Store the device in a clean area, away from sources of disturbance to avoid damage to the device.

#### 4.10.3 Distribution of Study Device

Biotronik will be providing the devices for implantation and no less than 5 devices will be stored for this specifical study protocol. Regular device inventory audits will be performed. This is done to ensure a sufficient supply for the study as well as ensure proper tracking of devices received and used.

#### 4.10.4 Return or Destruction of Device

The device will not be used if the packaging is wet, punctured, opened or damaged because the integrity of the sterile packaging may be compromised. The device will not be used if an unpackaged insertable cardiac monitor is dropped onto a hard surface, The device will not be used if there noted damage on opening the package, or if the device is expired. All devices will be returned to Biotronik in exchange for a functional device. All device serial numbers will be recorded on implanation. At routine intervals and at the completion of the study, there will be a reconciliation of devices shipped, devices utilized, and devices remaining. This reconciliation will be logged on the Device Accountability form, signed and dated. Any discrepancies noted will be documented, the sponsor-investigator will be notified and an investigation will be conducted to determine the cause of the discrepancy. Devices destroyed on site will be documented in the study files.

## 5 Study Procedures

Arrhythmias will be assessed via home monitoring through the Biomonitor 3 device. Superventricular tachycardia (SVT), ventricular arrhythmias (VA), bradycardia (<35bpm), heart block and atrial arrhythmias are considered of interest.

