## 2 Study Objectives

Listed below are the specific aims/objectives for this study.

**Specific Aim 1**: Burden of conduction system disease and arrhythmias, specifically sinus node dysfunction, high grade heart block, and AF and VA, which will identify those who might benefit from a PPM or ICD

**Specific Aim 2**: Mechanism of SCD (asystole, pulseless electrical activity, or sustained VA) and whether this is different in early vs. late stage amyloidosis.

**Specific Aim 3**: Risk factors for SCA and more specifically whether bradycardia or VA predict SCD, or whether there are imaging or clinical characteristics that predict SCA **Specific Aim 4**: Utility of long term ECG monitoring in TTR-wt cardiomyopathy

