#### 3.2 Primary Study Endpoints

1. Sudden cardiac death (including resuscitated cardiac arrest).

2. Syncope due to heart block or sinus node dysfunction requiring pacemaker

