#### 3.3 Secondary Study Endpoints

- 1. All-cause mortality: with a focus on HF deaths and bradycardia/PEA
- 2. PPM implantation and indication, frequent of pacing required, and if BIV pacing is needed
- 3. ICD implantation and indication, frequency of shocks and if appropriate vs inappropriate and if successful defibrillation occurred
- 4. Frequency of NSVT and predictability with other ventricular arrhythmias and sudden cardiac death
- 5. Frequency of atrial flutter or fibrillation and predictability with other arrhythmias including predictability of ventricular arrhythmias and sudden cardiac death

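### Silent heart block and NSVT counts depend on detection settings the plan never fixes, and the rhythm source can differ between the two stage groups being compared

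*Combined protocol and SAP*

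**What the plan says.** - **Outcomes.** Aim 1 (section 2) concerns the burden of conduction disease and arrhythmia, "specifically sinus node dysfunction, high grade heart block, and AF and VA, which will identify those who might benefit from a PPM or ICD". Secondary endpoint 4 (section 3.3) is "Frequency of NSVT and predictability with other ventricular arrhythmias and sudden cardiac death". The second primary endpoint (section 3.2) is "Syncope due to heart block or sinus node dysfunction requiring pacemaker".
- **Rhythms of interest.** Section 5: "Superventricular tachycardia (SVT), ventricular arrhythmias (VA), bradycardia (<35bpm), heart block and atrial arrhythmias are considered of interest". The bradycardia rate is the only numeric limit, and it is given as a definition, not as a device setting.
- **What the monitor classifies.** Section 4.5: "Arrhythmia may be classified as atrial fibrillation (AF), bradyarrhythmia, asystole, sudden rate drop, or high ventricular rate". Section 1.2 gives the same list as the device's indications.
- **How detection is set.** Section 4.5 calls the device programmable and adds: "The programmer is used to set up the Biomonitor 3 to detect arrhythmias". No section gives a detection rate, pause length, duration or beat count, or requires the same settings for every patient.
- **What is stored.** Section 4.5: "The device memory can store up to 30 min of subcutaneous ECG (sECG) recordings from automatically detected arrhythmias". Patient-triggered recordings have a further 30 minutes. Section 4.7 adds a daily transmission with a trend report whose contents are not described.
- **Second rhythm source.** Section 4.1 admits stage I-III patients who already have a pacemaker or defibrillator. Section 5 says that for stage III patients with such devices the rhythm data come from the device and may be retrospective. These devices are interrogated at enrollment and at six months, with interim records if available.
- **Analysis.** Section 6.2 compares arrhythmia burden between stage I-II and stage III by Student's t-test, taking in patients with any implanted cardiac device. Section 6.1 gives the purpose as assessing true burden.

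**The concern.** A count of silent episodes is a count of what the device was set to notice. If the limits are not stated, the frequency of NSVT or silent heart block cannot be interpreted in absolute terms, and a later trial cannot reproduce it.

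The more serious consequence is for the one planned comparison. If part of the stage III group is observed through pacemakers or ICDs with their own clinical settings, and stage I-II mainly through the Biomonitor 3, a difference in recorded burden may reflect the device and not the disease. An episode that was never stored cannot be recovered at review.

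**Working it through.** **Step 1. Set outcomes against detection classes.**

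| Rhythm | Role in the plan | Automatic class? | Limit stated? |
|---|---|---|---|
| High-grade heart block | Aim 1 | None; may trip bradyarrhythmia, asystole or rate drop | No |
| NSVT | Secondary endpoint 4 | None; may trip high ventricular rate | No |
| Bradycardia | Of interest | Yes | <35 bpm, as a definition only |
| AF | Aim 1, secondary endpoint 5 | Yes | No |

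**Step 2. Follow a silent episode.** Without symptoms there is no patient trigger. The episode is then stored only if it meets a programmed class. Block that stays above the low-rate setting without a pause, or NSVT slower or shorter than the high-rate setting, would leave no automatic tracing. The investigators' monthly review covers stored tracings. Automatic ECG memory is 30 minutes, which is 30/1440 = 2.1% of a day. The plan does not say when memory is cleared, so no loss figure follows from this.

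**Step 3. Follow the rhythm source by stage.** Section 5 names device-derived rhythm data for stage III only, and section 6.2 pools all devices. For retrospective records, the settings were fixed before the study and cannot be chosen.

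**Step 4. Illustrate the size.** The plan gives no burden, SD, alpha or event rate, so there is no figure to reproduce. From the plan: 25 per group. Assumed: equal true mean burden in both groups (set to 1), coefficient of variation c, group-average capture s1 and s2, two-sided alpha 0.05, normal approximation.

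- Difference in recorded means: d = |s1 − s2|
- SD = c × √[(s1² + s2²)/2]
- SE = SD × √(2/25)
- Chance of a significant result = Φ(d/SE − 1.96) + Φ(−d/SE − 1.96)

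Worked case, c = 1.0, 90% against 70%: d = 0.20; SD = √[(0.81 + 0.49)/2] = 0.806; SE = 0.806 × 0.283 = 0.228; d/SE = 0.877. The chance is Φ(−1.083) + Φ(−2.837) = 0.139 + 0.002 = 14%.

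| Capture | c = 0.5 | c = 1.0 | c = 1.5 |
|---|---|---|---|
| 90% v 70% | 42% | 14% | 9% |
| 90% v 50% | 97% | 49% | 25% |
| 90% v 30% | 100% | 89% | 56% |

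**Step 5. Ask what each row requires.** Suppose the Biomonitor 3 captures 90% and existing devices capture a share e, with a fraction q of stage III observed through existing devices. Average stage III capture is 0.9(1 − q) + eq.

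- 70% arises with q = 0.5 and e = 0.5: 0.45 + 0.25.
- 50% arises with q = 0.5 and e = 0.1: 0.45 + 0.05.
- 30% needs q of at least two thirds even if e = 0, since 0.9 × 1/3 = 0.30.

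The lower rows are therefore demanding. Mixing devices within a group also adds variance that the formula ignores. The documents do not say whether existing devices would capture more or less than the Biomonitor 3, so the direction of bias is unknown.

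**The case against.** The best defence has four parts.

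- **Settings may be uniform in practice.** This is a single-centre study, all implants are done in one unit, and the study investigators review the telemetry. A reader might infer that settings vary from patient to patient. The plan does not say so; it is silent. With one set used throughout, Biomonitor 3 patients would be comparable with one another. This stands, but absolute frequencies would still depend on unstated limits, and existing devices would remain outside that set.
- **The monitor does not store only automatic detections.** Patients can trigger recordings and a daily trend report is sent. This stands, so the point is limited to silent episodes.
- **The primary endpoints are mainly clinical.** Sudden death has a clinical definition, and syncope requiring a pacemaker is a symptomatic, treated event. A reader might infer that the primary endpoints are compromised; the documents do not support that. SVT is likewise only of interest and is not a listed endpoint.
- **Any numerical size is invented.** A fold-change in NSVT frequency between two high-rate limits needs an assumed distribution of NSVT rates, which the documents do not give, so none is claimed here. The table above is also an illustration, and no section shows that capture differs by stage.

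It is also fair that this is a descriptive pilot and that the reference to true burden sits in the sample-size rationale. Even so, section 6.1 offers the results as the basis for larger trials, and section 6.2 makes a formal comparison by stage.

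**Conclusion.** The concern holds in limited form. Silent high-grade heart block and NSVT have no automatic class on the Biomonitor 3, no common detection settings are stated, and the settings are not tied to the plan's own bradycardia definition. Their recorded frequencies are therefore conditional on unstated limits. Because existing pacemakers and ICDs may supply rhythm data, are named for stage III, and are pooled in the t-test, detection can be confounded with stage.

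The size of the bias cannot be derived from the documents. In the illustration, the chance of a false difference runs from 9% to nearly 100% against a nominal 5%, depending wholly on assumed capture and variability. It returns to about 5% if average capture is the same in both groups. The conclusion that detection can differ by stage rests on the text and does not need those figures. This should be corrected before data accrue; it does not undermine the clinical primary endpoints.

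**What to change.** 1. **Biomonitor 3.** Add a one-page sheet with one common set of detection settings. The investigators choose the values, which should ensure that the study's own bradycardia definition is recorded. Log any change required by care, with its date.
2. **Existing pacemakers and ICDs.** Record their detection limits on the CRF. Compare tachyarrhythmia counts such as NSVT between stages only above limits common to both device types. Where no common limit exists, report by device type and leave those data out of the stage comparison. Do the same for bradycardia and heart block in patients with a pacing device: pacing prevents the slow rhythm being counted, so a common limit cannot restore comparability.
3. **Reporting.** Present NSVT and asymptomatic heart block as minimum frequencies above the stated limits, not as true burden, and amend section 6.1 to match.

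The cost is one page, a few CRF fields and some wording. The real downside is that some recorded episodes drop out of the between-stage comparison in a study of 50 patients. They can still be reported descriptively by device type.
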